THE FEASIBILITY OF USING THE ULTRAVISION™ SYSTEM TO FACILITATE LOW IMPACT LAPAROSCOPIC SURGERY FOR THE TREATMENT OF ENDOMETRIOSIS

Study Summary

Introduction and Background

The Ultravision™ System is an FDA-cleared medical device that removes surgical smoke by means of electrostatic precipitation from the visual field during laparoscopic surgical procedures. “Surgical smoke” refers to the suspended particulate matter that is generated as a by-product of the combustion and other processes that are associated with the use of energy-based surgical instruments. Surgical smoke can obscure (partially or totally) the surgeon’s view of the operative field and this has obvious safety implications for the patient. In the case of laparoscopic procedures, which are increasing in popularity, the smoke is retained within the “closed abdomen” and this, coupled with the CO₂ pneumoperitoneum, presents additional challenges for the surgical team. The Ultravision™ System can therefore be considered an accessory to electrosurgical instruments to clear the surgical smoke generated during their use and as such will only be used when such devices are in use.

The ability to operate under “low impact” laparoscopic conditions has been shown by others to improve clinical outcomes by, for example, reducing post-surgical pain and with smaller incision sizes, improved cosmesis. For the purposes of this study “low impact” is defined as (1) a target pneumoperitoneal pressure of 10mm Hg; and (2) instead of 10mm and/or 12mm ports, the use of 3mm ports and one 5mm port. Using a standard insufflator, the combination of lower pneumoperitoneal pressure and smaller size ports creates visualization challenges for the surgeon due to the difficulty of preventing the buildup of surgical smoke within the abdomen. “Venting” or actively extracting the smoke through a trocar is known to be largely ineffective due to the narrow internal diameter of 3mm trocars, certainly unless the instrument is removed beforehand, which creates additional surgical challenges. Furthermore, operating under lower pressure can cause pneumoperitoneum to be lost upon venting of the smoke. The research question that is posed in this study is whether the Ultravision™ System, due to its unique mode of action which (unlike other smoke management approaches) provides smoke management without needing to extract or exchange CO₂, provides effective visual field clearing, thereby facilitating low impact laparoscopic surgery when using a conventional insufflator. In addition, Ultravision™ does not require CO₂ removal and replacement to achieve its intended use, thereby minimizing to the greatest extent possible patient CO₂ exposure. CO₂ is dry (effectively 0% relative humidity) and cold (typically 65F) and exposure is linked to postoperative pain and other adverse consequences such as patient cooling and tissue desiccation. Due its mode of action, Ultravision™ minimizes CO₂ exposure to the patient.

Laparoscopic surgery for the treatment of endometriosis is a common procedure for the removal of mild to moderate endometriosis. Diathermy is commonly used to remove the lesions which can be extensive, therefore this procedure presents an appropriate surgical procedure for this study.

Assessments in terms of surgical field visualization, CO₂ consumption, end tidal CO₂, patient satisfaction for cosmesis, and postoperative pain will be conducted in order to determine if the Ultravision™ System is effective in enabling laparoscopic surgery under low impact laparoscopic conditions. Adverse event information will be reported. The study is an open label single arm study.

Study Purpose

There are five main study objectives:

1. Demonstrate the feasibility of undertaking low impact laparoscopic surgery for endometriosis when using the Ultravision™ System.
2. Assess the impact of Ultravision on visual field clarity.
3. Determine the ability to complete the procedure while maintaining an abdominal pressure of \leq 10mmHg.
4. Quantify the consumption of CO₂.
5. Collect data on additional clinical outcomes associated with the use of Ultravision and low impact surgery (i.e. end tidal CO₂ levels (EtCO₂), adverse events, cosmesis outcome, postoperative pain levels and pain medications).

Study Hypothesis

The primary hypothesis being tested in this study is that Ultravision facilitates the utilization of low impact laparoscopic surgery techniques whilst maintaining an adequate visual field throughout the procedure with low demand for CO₂ replenishment to maintain pneumoperitoneal pressure.

Study Population

The study will enroll patients indicated for laparoscopic surgery to treat endometriosis. Patients must meet all inclusion/exclusion criteria.

Study Design

This is a prospective single arm study. The study will enroll 20 patients. Comparisons to prior clinical trials and published literature will be made to assess the relative significance of the study results.

Study Endpoints

Success will be based on demonstration that the procedures using the Ultravision™ System achieves the following endpoints :

1. The ability to complete the procedure without increasing pneumoperitoneum due to visualization.
Any increase beyond 10mm Hg and the reason for change will be recorded.
2. The quality of visualization in the laparoscopic field of view will be assessed by the investigator using a Visual Analog Scale (VAS).
3. Patient satisfaction with cosmesis outcome at the discharge follow-up visit assessed by means of a survey scaled from “very unsatisfied” to “very satisfied.”
4. Post-Surgery Pain assessment based upon a Numerical Rating Scale (NRS) where 0 is “no pain at all” to 10 “worst pain imaginable” and the location of the pain using a body diagram.
5. Pain medication utilization

Other Data Collection

- End tidal CO₂ volume (etCO₂) (taken at the start of the procedure and at the completion of the procedure),
- Adverse Events,
- Electrosurgical instrument(s) used,
- Preoperative assessment: patient demographics, medical history, medication information, height and weight, pain (at intake visit)
- Number of endometriosis lesions resected

Study Size:

A sample size of 20 patients should provide a sufficient sample size for comparative analysis to prior clinical data relative to Ultravision and published peer reviewed clinical data on laparoscopy and low impact laparoscopy.

Duration of Study:

The target for the overall duration of the study is four months.

Data Analysis: Descriptive statistics for all endpoints will be applied to analyze the results.

Results from other studies conducted by Alesi as well as clinical data gleaned from the medical literature will be used to assess the relative significance of the study result.

1. STUDY PROTOCOL INTRODUCTION & BACKGROUND

The advantages of laparoscopic surgery are generally accepted in the medical community. However, as with any therapy or procedure the unique circumstances associated with this type of surgery are not without physiological consequences such as tissue desiccation and postoperative pain.^{1 2} The working space created by pneumoperitoneum using CO₂ is required to create the visual/working field but creates its own concerns regarding abdominal pressure and CO₂ absorption into the abdominal tissue.³ The smoke generated by electrosurgical devices in the process of dissection of tissues during laparoscopy can obscure the surgical visual field which can impede the operating surgeon. It is often necessary to suspend the surgery to allow the smoke to dissipate, or more commonly open a laparoscopic port to vent the smoke into the room, adding to the operating time. It is also common to remove the laparoscope to clean the lens because it can be soiled by the smoke as well. In order to enhance the dissipation of smoke and maintain an adequate pneumoperitoneum it is often necessary to increase the flow of carbon dioxide (CO₂) from the insufflator. Surgical smoke handling during laparoscopic surgery results in an increase of the known risks to the patient of using excessive CO₂ as well as exposing the operating room staff to the smoke which may create a potential health concern.

The Ultravision™ Visual Field Clearing System provides a stable and clear visualization using electrostatic precipitation to remove the smoke from the visual field. This is accomplished with Ultravision without requiring venting of gas, that would otherwise be replaced to maintain the pneumoperitoneum operating pressure. Because it does not rely on gas flow for smoke clearing, CO₂ consumption is greatly reduced compared to other methods. Safety and feasibility studies have been carried out allowing it to be placed on the market in Europe, Japan and the United States. A randomized study of its clinical effectiveness showed that electrostatic-precipitation significantly improved visibility (reduction of visual impairment) and reduced

¹ O'Malley C, Cunningham AJ, Physiologic Changes during laparoscopy, Anesthesiology Clinics of North America, 2001 Mar; 19(1): 1-19.

² Veekash G, Wei LX, Su M, Carbon dioxide pneumoperitoneum, physiologic changes and anesthetic concerns, Ambulatory Surgery, 162 July 2010.

³ Srivastava A, Niranjan A, Secrets of laparoscopic surgery: Anaesthetic and surgical considerations, Journal of Minimum Access Surgery, 2010 Oct-Dec; 6(4): 91-94.

surgery time in laparoscopic cholecystectomy.⁴ A similar study in laparoscopic hysterectomy and myomectomy reported similar results at lower pneumoperitoneal pressures (10mmHg).⁵

The ability to operate under low impact laparoscopic conditions has been shown by others to improve clinical outcomes by, for example, reducing post-surgical pain and improved cosmesis.⁶ For the purposes of this study “low impact” is defined as (1) a target pneumoperitoneal pressure of 10mm Hg; and (2) the use of 3mm ports with one 5mm port. Using a standard insufflator, the combination of lower pneumoperitoneal pressure and smaller size ports creates visualization challenges for the surgeon due to the difficulty of preventing the buildup of surgical smoke within the abdomen. “Venting” or actively extracting the smoke through a trocar is known to be largely ineffective due to the narrow internal diameter of 3mm trocars, certainly unless the instrument is removed beforehand, which creates additional surgical challenges. In addition, due to its unique mode of action, Ultravision™, unlike other smoke clearing systems, does not require CO₂ removal and replacement to achieve its intended use. CO₂ exposure is linked to postoperative pain and other adverse consequences (i.e. patient cooling, tissue desiccation). Due to its mode of action, Ultravision™ minimizes CO₂ exposure to the patient.

Laparoscopic surgery for the treatment of endometriosis is a common procedure for the removal of mild to moderate endometriosis. Diathermy is commonly used to remove the lesions which can be extensive, therefore this procedure presents an appropriate surgical procedure for this study. Diathermy devices are electrosurgical devices that deliver high frequency currents to heat tissue to aid in dissection of tissue and to control bleeding.

⁴ Ansell J., Electrostatic precipitation is a novel way of maintaining visual field clarity during laparoscopic surgery: a prospective double-blind randomized controlled pilot study. *Surg, Endosc.* (2014) 28: 2057-2065)

⁵ Levine D., Investigator sponsored research, “ A randomized, controlled study evaluating the effectiveness of the Ultra vision™ Visual Field Clearing System in laparoscopic hysterectomy and myomectomy,” Mercy Hospital St. Louis, November 2018.

2. STUDY PURPOSE

The research question that is posed in this study is whether the Ultravision™ System provides effective visual field clearing thereby enabling low impact laparoscopic surgery when using a conventional insufflator with low demand for CO₂ replenishment to maintain pneumoperitoneal pressure.

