7. STUDY SIZE

The study will enroll 20 patients.

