11.2. EXCLUSION CRITERIA

Subjects MUST not have any of the following:

E1	Existing comorbidities that would contraindicate them for laparoscopic surgery.
E2	Patient anatomy that is not compatible with the use of the Ionwand catheter i.e. abdominal wall thickness that exceeds the working length of the Ionwand catheter identified intraoperatively
E3	Patient with a BMI >50
E4	Be pregnant

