13. SCREENING & ENROLLMENT

Patient demographics and other baseline information will be collected to establish whether the patient meets the requirements for the study. It is assumed that a physical exam will be conducted as part of the standard of care. Only limited information on the patient's health status is collected for the study as defined in Table 1 below. Each patient will be assigned a unique study number. Baseline information will be collected, consistent with the standard of care. Baseline assessment is conducted at the preoperative visit.

Table 1
Baseline Assessment – Conducted at Pre-op visit

Type of Information	Data Sources	Time Frame
Date of Evaluation	Investigator Report	NA
Subject Age	Subject interview / Medical Record	NA
Height	Medical Record	NA
Weight	Medical Record	NA
Body Mass Index (BMI)	Medical Record	
Prior/Existing Medical Conditions	Subject interview & medical record	Within three months prior to surgery
Prior/Existing Medical Interventions	Subject interview & medical record	Within three months prior to surgery
Diagnosis Indicating Surgical Intervention	Investigator Report	Within three months prior to surgery
Current Pain Medications and Reason for Taking	Subject interview & medical record	Within three months prior to surgery

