15. PROCEDURE PROTOCOL

The device is used in accordance with the instructions for use. An initial target pneumoperitoneal pressure setting of 10mmHg will be used for the procedure. At the discretion of the surgeon investigator, pressure will be adjusted as needed to accomplish the surgical procedure. A standard insufflator with 3mm ports and one 5 mm ports will be used for the procedure.

Table 3
Intraoperative/Procedure Information

Type of Information	Time Point	Data Sources
Date of Procedure	Before opening	Patient Medical Record
Pneumoperitoneum pressure after camera trocar is inserted	Intraoperative	Investigator Report
Increase in pressure and reason for change	Intraoperative	Investigator Report
Adverse Events	Intraoperative	Investigator Report
Unplanned concomitant interventions or procedures	Intraoperative	Investigator Report
End tidal volume of CO ₂ (etCO ₂), recorded at the beginning and end of the procedure.	Intraoperative	Investigator Report
Number of CO ₂ liters consumed	At completion of the procedure	Investigator Report
Surgeon Survey on Quality of Visualization and Smoke Management	Immediately Post-operative	Investigator Report
Ultravision device(s) used (lot# and model #)	Immediately Post-operative	Investigator Report
Diathermy device(s) used	Immediately Post-operative	Investigator Report
Device Malfunction – recorded as an adverse event	Intraoperative	Investigator Report
Number of Endometriosis Lesions Resected	Post-operative	Operative Report / Investigator Report
Pain Assessment	Just Prior to discharge	Medical Record

Table 3
Intraoperative/Procedure Information

Type of Information	Time Point	Data Sources
Pain Medications	Prescribed at discharge	Medical Record

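### The hypothesis is about CO₂ replenishment, but the only insufflated volume scheduled is total litres at the end, which cannot be split into initial fill and replenishment

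*Protocol*

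**What the plan says.** The CO₂ part of the research question in Protocol Section 2 reads "with low demand for CO₂ replenishment to maintain pneumoperitoneal pressure". The Study Hypothesis paragraph of the Study Summary uses the same words. Objective 4, under Study Purpose in the Study Summary, is worded differently: "Quantify the consumption of CO₂".

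Table 3 in Section 15 lists what is recorded in theatre. Three items bear on this point:

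- "Number of CO ₂ liters consumed", once, at completion of the procedure.
- "Pneumoperitoneum pressure after camera trocar is inserted", which is a pressure and not a volume.
- End tidal CO₂, "recorded at the beginning and end of the procedure", which is a respiratory measure and not a volume of insufflated gas.

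The table has no litre reading when the target pressure is reached, no interim reading and no record of refills. Section 25.2 says that results will be summarised descriptively and set against other company studies and the literature.

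**The concern.** The background in Section 1 explains the expected benefit: smoke is cleared without venting, so gas does not have to be put back to hold the pressure. Replenishment is therefore what is added after the abdomen has been inflated. The gas that inflates it in the first place is not replenishment, and smoke clearance should not affect it.

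If only the sum of the two is recorded, the quantity named in the hypothesis is not observed for any patient. Because the trial has a single arm, whether demand was low will be judged mainly against outside figures. In such a comparison the two components cannot be told apart. A reading not taken during surgery cannot be recovered later by any analysis.

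**Working it through.** The protocol states no CO₂ volume, so there is no figure of its own to reproduce. The check is an identity followed by assumed ranges.

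**Identity.** Let T be total litres, F the initial fill (plus any full refill) and R replenishment. Then T = F + R. Only T is scheduled, which leaves one equation with two unknowns. Since F is not negative, R ≤ T.

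**Fill as a share of the total, F / (F + R).** All inputs are assumptions: F = 2 to 5 L, and maintenance use of 0.1 to 0.5 L/min over 40 minutes, so R = 0.1 × 40 = 4 L to 0.5 × 40 = 20 L.

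| F (L) | R (L) | T (L) | F / T |
|---|---|---|---|
| 2 | 20 | 22 | 9% |
| 5 | 20 | 25 | 20% |
| 2 | 4 | 6 | 33% |
| 5 | 4 | 9 | 56% |

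**Wider assumed range, F = 2 to 6 L.** The share is 50% to 75% at R = 2 L, 29% to 55% at 5 L, 17% to 38% at 10 L, 9% to 23% at 20 L and 5% to 13% at 40 L.

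**What a recorded total implies, R = T − F, with F = 2 to 6 L.** A total of 8 L fits R from 2 to 6 L, 10 L fits 4 to 8 L, 25 L fits 19 to 23 L and 45 L fits 39 to 43 L. The width is always 6 − 2 = 4 L. The relative uncertainty grows as replenishment falls, but the absolute uncertainty does not.

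**Outside comparison.** The difference in totals equals the difference in F plus the difference in R. With the same assumed R = 8 L and fills of 2 and 5 L, the totals are 10 and 13 L. That is a ratio of 1.30 with no difference in replenishment.

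**The case against.** The strongest reply is that the stated CO₂ objective is consumption, and total litres answers it directly. The introduction also argues in terms of the patient's overall CO₂ exposure, of which the fill is a part. This stands: the mismatch is with the replenishment clause of the hypothesis and research question, not with Objective 4.

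Second, the total is an upper bound. A small total is evidence of low replenishment, and ignoring the fill overstates demand within this trial, which is the cautious direction. This also stands. A reader might infer that the hypothesis cannot be addressed at all, or that the measure fails just where the hypothesis is true; neither follows. The bound does not, however, remove differences in fill from outside comparisons, and the protocol sets no threshold for low.

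Third, a reader might infer that body size distorts the result, since the only size limit is "Patient with a BMI >50", or that a smaller fill at 10 mmHg would be credited to the device. The protocol supports neither as fact. It says nothing on how fill relates to body size, and an eligibility limit does not show the spread enrolled. Height, weight and "Body Mass Index (BMI)" are collected at baseline (Table 1), so totals can be described by body size, although this does not recover the fill. The CO₂ comparators are not named, and Section 1 cites an earlier study of the device at 10 mmHg.

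Fourth, the protocol does not say whether the recorded litres include the fill, and the CRFs are a separate document. Inclusion is the natural reading of the item, and Section 23 requires the CRFs to reflect the plan, which has no fill reading.

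Finally, CO₂ volume is not among the listed success endpoints and the analysis is descriptive, so no formal decision turns on it. That limits the weight of the point.

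**Conclusion.** The point holds as a gap between the quantity named and the quantity recorded. The hypothesis and research question concern replenishment; the plan records one insufflated volume, which bounds replenishment from above but cannot be separated from the fill. Objective 4 is served as it stands.

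How much this matters depends on volumes that the protocol does not give. Under the assumed 2 to 5 L fill and 4 to 20 L replenishment, fill is about 9% to 56% of the total, which runs from minor to substantial. The conclusion also rests on reading the recorded litres as including the fill. It is a cheap improvement to make before data are collected, not a flaw that invalidates the study.

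**What to change.** In Table 3, add the insufflator's cumulative litre reading when the target pressure is first reached. Note any full desufflation and refill, with the reading before and after. For the hypothesis, report replenishment = final reading − first reading − refills. Keep total litres for Objective 4 and for comparison with sources that report only totals. State in the table that the total includes the initial fill.

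The cost is one or a few extra display readings and the matching CRF fields, in a study where "The study will enroll 20 patients". There are two limits. Outside comparison of replenishment is restricted to sources that report it. The difference would also still include gas lost at ports and during instrument exchange, so it measures replenishment and not the smoke-related part of it.

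If no further reading is wanted, reword the hypothesis and the research question to total CO₂ consumption, which the planned reading does measure.

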3. INTENDED USE (PER INSTRUCTIONS FOR USE)

The Ultravision™ System is indicated for the clearance of smoke and other particulate matter that is created during laparoscopic surgery.

4. DEVICE DESCRIPTION

The Ultravision™ System is an accessory to electrosurgical instruments that is used to clear the surgical smoke generated during their use and as such will only be used when such devices are in use. An example of the effect of the Ultravision™ System during use to improve the visualization of the field of view is demonstrated in Figure 2 below:

[figure not shown]

Figure 1. View before and during cutting with an electrosurgical instrument

Figure 2. Electrosurgical smoke without (left hand image) and with (right hand image) Ultravision.

The system includes the following elements:

Standalone battery-operated generator unit

Figure 3. Ultravision Generator with battery pack

Ionwand™, which is introduced into the abdomen of the patient through either the Ultravision™ 5mm Trocar or a 2.5mm percutaneous catheter and provides the source of the electrons that create the negative ions that transiently charge the surgical smoke particles.

Figure 4. Ionwand, sterile assembly in package (top), 5mm Trocar (bottom)

Other accessories include a patient return adaptor and battery recharging station.

5. US REGULATORY STATUS

The Ultravision™ System obtained regulatory clearance through US FDA's De Novo Classification Process (DEN 150022). The system has been in distribution in Europe since January 2014 and in the US since December of 2016, over 250 systems are currently in use. To date there have been no incident or medical

device reports (patient injury reports) and there have been no product recalls. The Ultravision™ System and consumable items are being provided for this study free of charge.

